### Screening/selection

Both researchers and teachers will motivate parents/caregivers and children to enrol in all scientific measurements. Researchers will visit every childcare centre to inform teachers and children about the measurements. Children from study years four to six will receive a brochure from researchers with information about the research that is appropriate for their parents/caregivers as well as for themselves. Experience from the HPSF trial showed that this personal approach of researchers directly motivating children and teachers facilitated recruitment of participants. Besides motivating children and teachers through childcare centre visits, researchers will join regular, already-planned information meetings for parents at the childcare centres. If needed, new information meetings for parents will be organised as well. In this way, parents will be informed and encouraged to participate in the research.

### Inclusion- and exclusion criteria

In order to be eligible to participate in the study, a subject must meet all of the following criteria:

- Student of study year four to six at one of the participating childcare centres of Prisma;
- Informed consent signed by both caregivers.

No exclusion criteria are applicable as this is a real-life study and all students who meet the inclusion criteria will be included for participation in this study.

### Number of anticipated participants

Childcare centres are free to choose if, when and to what degree they implement HCCF changes in their childcare centre. After data collection, the twelve childcare centres will be divided into three categories based on the Diffusion of Innovations theory (innovators/early adopters, early/late majority, laggards) (35). Because this categorisation occurs after data collection, it cannot yet be predicted which childcare centres will fall under which category. However, based on the childcare centres' intentions that have become clear during preliminary discussions about the project, three potential scenarios can be illustrated where childcare centres are categorised within the three groups. These scenarios are further illustrated in the light of three sample size calculations that allow for clustered sampling. For the calculations, the following website is used: <http://www.sample-size.net/means-effect-sizeclustered/> (36).

The sample size calculation was based on the primary outcome, i.e. to detect a difference in mean absolute BMI z-score between innovators/early adopters and laggards after two years intervention. The following general assumptions were used for the sample size calculation:

- Independent-samples t-test on difference in absolute BMI z-scores;
- Children are nested within schools;
- A significance level (alpha) of 0.05;
- A power of 80%;
- A dropout rate of 10%, as based on dropout rates observed by Bartelink et al.(33);
- An Intraclass Correlation Coefficient of 0.01, as based on Amorim et al. (37);
- Unequal cluster sizes with a relative efficiency of 90% (38);
- An average absolute BMI-z of 0.76 and an SD of 0.60 in the population (as no data was available for the population in Peel en Maas, these values were calculated over all children aged between 4 and 11 living in region Parkstad who visited the Youth Health Department in 2013).

### Scenario 1

- *Innovators/early adopters*: three childcare centres, number of participants (N1)=120
- *Laggards*: four childcare centres, number of participants (N3)=220
- Average size of each cluster (m): 50
- With these assumptions we can demonstrate a Cohen's d of **0.369**, which means we can detect medium effect sizes on absolute BMI z-scores. A difference in mean absolute BMI z-score of **0.22** between innovators/early adopters and laggards can be detected. The detection of this difference is feasible in this population, as in a school-based longitudinal study with comparable intervention components, a mean difference between intervention and control group of -0.26 (CI 95%: 0.32, -0.21) BMI z-score was found (39).

### Scenario 2

- *Innovators/early adopters*: four childcare centres, number of participants (N1)=217
- *Laggards*: four childcare centres, number of participants (N3)=217
- Average size of each cluster (m): 55
- With these assumptions we can demonstrate a Cohen's d of **0.331**, which means we can detect medium effect sizes on absolute BMI z-scores. A difference in mean absolute BMI z-score of **0.20** between innovators/early adopters and laggards can be detected. The detection of this difference is feasible in this population, as in a school-based longitudinal study with comparable intervention components, a mean difference between intervention and control group of -0.26 (CI 95%: 0.32, -0.21) BMI z-score was found (39).

### Scenario 3

- *Innovators/early adopters*: four childcare centres, number of participants (N1)=217
- *Laggards*: five childcare centres, number of participants (N3)=303
- Average size of each cluster (m): 55
- With these assumptions we can demonstrate a Cohen's d of **0.314**, which means we can detect medium effect sizes on absolute BMI z-scores. A difference in mean absolute BMI z-score of **0.19** between innovators/early adopters and laggards can be detected. The detection of this difference is feasible in this population, as in a school-based longitudinal study with comparable intervention components, a mean difference between intervention and control group of -0.26 (CI 95%: 0.32, -0.21) BMI z-score was found (39).

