**Main parameters/endpoints:** The main study parameter of the effect evaluation is the change in absolute BMI z-score, which will be compared between the childcare centres that are categorised based on their degree of implementation (using categories based on the Diffusion of Innovations Theory).

**Methods:** Data will be collected in the form of questionnaires (parents, children, teachers/pedagogical employees, directors), anthropometric measurements (children), interviews (teachers/pedagogical employees, directors), observations and analyses of minutes of meetings.

**Nature and extend of the burden and risks associated with participation:** No intervention is allocated in this study other than activities planned by childcare centres in accordance with wishes and needs of childcare centre staff and parents. All outcome measures are non-invasive. The measurement protocol was designed while taking into account both a minimal burden for participants and a relevant scientific output for stakeholders (e.g., school board, teachers, parents/caregivers and children). Burden of participants is minimised by incorporating most measurements in the regular school day.

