### Effect evaluation:

- *Primary outcome:* At two-year follow-up, is there a difference in absolute BMI z-score between children from different childcare centres, which have been categorised based on their level of innovativeness and implementation?
- *Secondary outcomes:*
  - ➔ At two-year follow-up, is there a difference in waist/hip circumference between children from different childcare centres, which have been categorised based on their level of innovativeness and implementation?
  - ➔ At two-year follow-up, is there a difference in physical activity behaviours of children from different childcare centres, which have been categorised based on their level of innovativeness and implementation?

- ➔ At two-year follow-up, is there a difference in dietary behaviours of children from different childcare centres, which have been categorised based on their level of innovativeness and implementation?
  - ➔ At two-year follow-up, is there a difference in health markers of children from different childcare centres, which have been categorised based on their level of innovativeness and implementation?
- At two-year follow-up, is there a difference in school well-being of children from different childcare centres, which have been categorised based on their level of innovativeness and implementation?

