## 2. METHODS

### 2.1 Study procedure/study design

The current study involves twelve childcare centres from the Prisma educational board, which are all located in Peel en Maas. The childcare centres are selected based on their expressed interest to participate in the project. The childcare centres are free to choose if, when and how they want to implement changes fitting HCCF. To study programme effectiveness, a non-randomised trial will be executed. Instead of true intervention and control childcare centres, after the project, the centres will be divided into groups based on their implementation phase. This division will be based on the Diffusion of Innovations Theory by Rogers (1995). According to Rogers, there are five types of adopters, which all have different adoption rates of a given innovation. From fast to slow adoption rate, these types of adopters are: innovators, early adopters, early majority, late majority and laggards. These adopters vary in adoption rate due to a difference in innovativeness; the degree to which an individual/organisation adopts a new idea (35). When looking at the Prisma childcare centres, it is likely that some childcare centres will adopt changes fitting HCCF earlier than others. Therefore, the different childcare centres can be categorised using Rogers' categories, which will facilitate comparison between the different childcare centres. It is expected that the childcare centres can be divided in three categories: innovators/early adopters, early/late majority and laggards.

The total study duration will be four years, of which roughly the first six months are preparation and the last year is evaluation. Therefore, data will be collected for approximately two years. Figure 1 provides an overview of the study.

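### Centres are sorted into the groups of the primary effect comparison after data collection, with no scoring rule, outcome-blind grading or lock, so outcome-influenced grouping is not excluded

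*Combined protocol and SAP*

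**What the plan says.** All references are to the combined protocol and SAP.

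- **When.** Section 2.1 says "after the project, the centres will be divided into groups based on their implementation phase". Section 2.2 (Number of anticipated participants) says the same, "After data collection, the twelve childcare centres will be divided into three categories based on the Diffusion of Innovations theory", and adds that membership cannot yet be foreseen.
- **On what basis.** The wording varies. The Summary has centres "categorised based on their degree of implementation (using categories based on the Diffusion of Innovations Theory". The research questions in section 1.1 have centres "which have been categorised based on their level of innovativeness and implementation". Section 2.1 speaks of implementation phase and introduces the categories by speed: "From fast to slow adoption rate, these types of adopters are".
- **How many, how large.** Section 2.1 expects three categories. Section 2.2 illustrates innovators/early adopters versus laggards as 3 versus 4, 4 versus 4 and 4 versus 5 centres. In Scenario 2, for example, the laggards are "four childcare centres, number of participants (N3)=217". These are presented as possible scenarios, not as fixed sizes.
- **Use.** Section 2.4 enters group, time and their interaction as fixed effects in a three-level mixed model.
- **Who.** Section 2.3 has the principal investigator, assistants and students collect all data. Section 2.5 (Data access) gives those involved in data collection access to the research data. No section says who grades the centres.
- **Process data.** Table 1 lists centre rules and practices, staff practices, interviews and observations. The Summary adds "observations and analyses of minutes of meetings". Nothing links any of these to a category.

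**The concern.** Grading centres once their implementation has been observed is unavoidable in this design and is not the fault. What is missing is anything that fixes how the grading is done or keeps it apart from the outcomes. With twelve centres and extreme groups of three to five, one centre is a fifth to a third of a group, so the placing of a borderline centre matters.

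If knowledge of BMI results affected that placing, a test at the nominal 5% level would be too liberal and the estimated difference would be shifted. Section 1 (Conclusion) also plans to link the effect results to the process evaluation and to compare them with the earlier trial, so the grouping carries forward into both. The main objective, the process evaluation, does not depend on this comparison.

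**Working it through.** **1. The plan's own figures.** Inputs from section 2.2: alpha 0.05 (two-sided assumed), power 80%, ICC 0.01, SD 0.60, cluster size m = 50 in Scenario 1 and 55 in Scenarios 2 and 3. With DE = 1 + (m − 1) × 0.01, n = centres × m and d = 2.80 × √[DE × (1/n1 + 1/n3)]:

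| Scenario | DE | n1, n3 | d | d × 0.60 | Plan |
|---|---|---|---|---|---|
| 1 | 1.49 | 150, 200 | 0.369 | 0.22 | 0.369; 0.22 |
| 2 | 1.54 | 220, 220 | 0.331 | 0.20 | 0.331; 0.20 |
| 3 | 1.54 | 220, 275 | 0.314 | 0.19 | 0.314; 0.19 |

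The stated figures are reproduced (without the dropout and relative-efficiency allowances) and are not disputed here.

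**2. Scale of one centre mean.** SD = 0.60 × √(0.01 + 0.99/55) = 0.60 × √0.028 = 0.100. The standard error of a 4 versus 4 difference is 0.100 × √(1/4 + 1/4) = 0.071, and 2.80 × 0.071 = 0.20, which agrees with Scenario 2.

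**3. One borderline centre, by hand.** Let one centre be in or out of the innovators/early adopters, giving 4 versus 4 or 3 versus 4.

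- The variances of the two differences, in units of the centre-mean variance, are 1/4 + 1/4 = 0.500 and 1/3 + 1/4 = 0.583. Their covariance is 1/4 + 1/4 = 0.500.
- The correlation of the two test statistics is 0.500/√(0.500 × 0.583) = 0.926.
- The chance that at least one exceeds 1.96 in absolute value under the null is 6.8%.
- The two estimates differ by (mean of the three − the fourth)/4, with SD 0.100 × √(1/3 + 1)/4 = 0.029. The median absolute gap is 0.674 × 0.029 = 0.02 BMI z.

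**4. Null simulation.** 400,000 draws of 12 independent, equal centre means; reject if the largest |difference|/SE over the open groupings exceeds 1.96.

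| What is left open | Groupings | Error rate | Median gap, largest minus smallest estimate (BMI z) |
|---|---|---|---|
| Nothing (4 v 4 fixed) | 1 | 5.0% | 0 |
| One borderline centre, in or out | 2 | 6.7-6.8% | 0.02 |
| One borderline centre at each cut, in or out | 4 | 8.4-8.9% | 0.03-0.04 |
| Sizes held at 4 v 4, two centres competing for one place at each cut | 4 | 10.4-10.5% | 0.05 |

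**5. Limits.** Every rate above 5% assumes that the most significant grouping is always taken. The number of borderline centres is an assumption; the documents give none. Centres are treated as equal in size, although Scenarios 1 and 2 imply otherwise: if nested, the fourth innovator/early-adopter centre would have 217 − 120 = 97 participants, against 120/3 = 40 for the others. With those sizes, one borderline centre gives 7.2%. Only two of the three groups are compared. The calculation is cross-sectional, whereas the Summary names change in absolute BMI z-score as the main parameter and section 2.4 fits repeated measures. The absolute gaps would therefore differ for change from baseline.

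**The case against.** **Grouping after the fact is the design.** True, and accepted. It explains the timing but not the absence of a rule, of blinding and of a lock.

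**The theory supplies the rule.** Section 2.1 gives ordered labels and defines innovativeness as how far an organisation adopts something new, which brings timing and degree closer together than the varied wording suggests. That part stands: the constructs need not conflict, and a stated composite would serve. But labels and a definition do not say which of twelve centres falls on which side of a cut.

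**The rule may be elsewhere.** Figure 1 is not shown and the data management plan is a separate document. The text describes the first as a study overview and the second as covering storage, sharing, preservation and security. Neither is said to hold a grading rule, so this is a caveat only.

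**The figures are worst-case.** This stands. A reader might infer that the error rate will actually be inflated, or reach much higher rates by assuming several borderline centres at each cut (26% with 36 open groupings). The documents support neither inference, because they give no number of borderline centres and no sign that outcomes will guide the grading.

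**The effect evaluation is secondary and openly non-randomised.** Also true. It limits the weight of the point but does not remove it.

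**Conclusion.** The point holds. The exposure of the primary effect comparison is assigned after data collection, and the visible plan has no operational rule, no outcome-blind grading and no lock, while one team collects all data and has access to it. Following the plan as written leaves the comparison open to outcome-influenced grouping.

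A reader might go further and conclude that the investigators mean to sort centres by their results. The documents do not support this: they do not say who will grade, and nothing suggests such an intention.

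As a worst-case illustration under the assumptions listed above, the 5% error rises to about 7% with one borderline centre and about 8-10% with one at each cut. At one per cut, the median spread of the estimate is 0.03-0.05 BMI z, roughly 15-25% of the 0.20 detectable in Scenario 2 (0.03/0.20 and 0.05/0.20). This is worth correcting, but it affects the effect evaluation rather than the main process objective.

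**What to change.** Before outcome data are analysed by group or centre:

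1. Write one centre-level scoring rule based on timing of adoption, degree of implementation or a stated composite of the two, with fixed cut-points or fixed group sizes. Use the process items already in Table 1 and the meeting minutes. Table 1 has no adoption-date item, so a timing component would have to come from interviews and minutes.
2. Have existing team members who have not seen outcome data summarised by centre score from those items only. The two qualitative coders in section 2.4 could do this if they meet that condition.
3. Remove outcome items from what the scorers receive. The teacher questionnaire, for example, combines class atmosphere and pupil behaviour, which are well-being outcomes, with health practices and appreciation of the project.
4. Date and lock the categories before outcomes are released to the scorers, and amend section 2.5 (Data access) accordingly.
5. Optionally, report the same model with the continuous score across all 12 centres as a sensitivity analysis.
6. State that confounding remains, because "The childcare centres are free to choose if, when and how they want to implement changes fitting HCCF". Locking the groups does not address it.

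**Cost.** A written rule, a dated file and a real separation of tasks within a team that now collects everything; no new measurements. Cut-points fixed in advance may fit the final spread of centres less neatly.

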#### **(Interim)analyses**

Linear mixed model analysis techniques will be used to assess the longitudinal effect of HCCF on numerical outcome variables, as this technique corrects for correlation within individuals within groups, which occurs in repeated-measures research designs. Another advantage of this technique is that it naturally handles missing values, in case data are missing at random. Since measurements are repeated within participants, who are nested within childcare centres, we use a three-level model with childcare centres as third level, participants as second level and measurements as first level. The fixed part of the model consists of group (distribution based on Diffusion of Innovations Theory), time (time-points at which the measurements are taken) and the interaction term group\*time. Baseline variables that are related to missing data and/or outcome will also be included to obtain unbiased results and/or to gain precision. As for the random part of the model, a random intercept on childcare centre level will be included next to an unstructured covariance structure for the repeated measurements.

For categorical outcome variables, a logistic mixed model analysis technique will be used, where the model is similar as described for the numerical outcome variables.

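### The detectable differences use normal quantiles although the contrast rests on 7 to 9 centres; with centre-level degrees of freedom, power at those differences is about 61 to 67%, not 80%

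*Combined protocol and SAP*

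**What the plan says.** Section 2.2, Number of anticipated participants, sizes the comparison of innovators/early adopters with laggards after two years. The listed assumptions include "Independent-samples t-test on difference in absolute BMI z-scores", "Children are nested within schools", "A significance level (alpha) of 0.05", 80% power and "An Intraclass Correlation Coefficient of 0.01", with an SD of 0.60, 10% dropout and 90% relative efficiency for unequal cluster sizes. A web calculator for clustered means is cited. No degrees of freedom are given.

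Three scenarios follow, with 3 v 4, 4 v 4 and 4 v 5 centres and average cluster sizes of 50, 55 and 55. They give d = 0.369, 0.331 and 0.314 (0.22, 0.20 and 0.19 BMI z), "which means we can detect medium effect sizes on absolute BMI z-scores". Each is called feasible because a comparable school study found a difference of 0.26.

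Section 2.4, (Interim)analyses, plans a three-level linear mixed model with group, time and group*time, in which "a random intercept on childcare centre level will be included next to an unstructured covariance structure" for the repeated measurements. A similar logistic model is planned for categorical outcomes. Neither has a stated denominator-df method.

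**The concern.** Centres, not children, are sorted into adoption groups. A design effect enlarges the variance to allow for clustering, but pairing it with 1.96 and 0.842 treats the between-centre variance as known. Here that variance must be estimated from a handful of centres. The reference distribution for the stated two-group test is then t with (number of centres − 2) df, and the loss is large at 5 to 7 df.

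Two things are at stake. A null result could be read as coming from a comparison with 80% power when the calculation described does not deliver it. And if the analysis itself used normal or child-level critical values, the test of a between-centre difference would be too liberal.

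**Working it through.** **Inputs (section 2.2).** ICC 0.01; SD 0.60; alpha 0.05 (sidedness is not stated; two-sided is confirmed by the reproduction); centres k1 v k3 = 3 v 4, 4 v 4, 4 v 5; m = 50, 55, 55.

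**Step 1: reproduce the plan.** DE = 1 + (m − 1) × 0.01 = 1.49, 1.54, 1.54. With centres × m children per group (150/200, 220/220, 220/275):

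SE = √[DE × (1/(k1·m) + 1/(k3·m))] = 0.1318, 0.1183, 0.1122

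d = (1.960 + 0.842) × SE = 0.36938, 0.33149, 0.31448

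These round to the stated 0.369, 0.331 and 0.314. Alternatives do not fit: t quantiles on child-level df give 0.3704, 0.3322 and 0.3151, and the printed group sizes (N1, N3) give 0.388, 0.334 and 0.309. So the plan used normal quantiles and centres × m, with no further reduction for dropout or relative efficiency.

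**Step 2: same inputs, centre-level df.** The noncentrality at the stated d is d/SE ≈ 2.80 in every scenario. Power comes from the noncentral t. The detectable difference is 0.60 × SE × (noncentrality needed for 80%).

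| | Scenario 1 | Scenario 2 | Scenario 3 |
|---|---|---|---|
| Two-group df | 5 | 6 | 7 |
| Critical value | 2.57 | 2.45 | 2.36 |
| Power at stated d | 61% | 65% | 67% |
| Noncentrality for 80% | 3.514 | 3.367 | 3.270 |
| Detectable d | 0.463 | 0.398 | 0.367 |
| Detectable BMI z | 0.28 | 0.24 | 0.22 |
| Power at 0.26 | 75% | 86% | 91% |

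Simulating a t-test on centre means (200,000 runs) gave 61.3, 64.8 and 67.0% power at the stated d.

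If all twelve centres in three groups estimate the centre variance (12 − 3 = 9 df, critical value 2.26, noncentrality 3.150), power at the stated d is about 70% in each scenario. The detectable differences are 0.25, 0.22 and 0.21, and power at 0.26 is 83, 90 and 93%.

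**Step 3: dropout and relative efficiency.** Step 2 includes neither. The text does not say whether the centres × m counts are before or after them. Assuming they are before both, and treating each as a factor on effective sample size, the factor is 0.9 × 0.9 = 0.81. The noncentrality becomes 2.80 × √0.81 ≈ 2.52. Power at the stated d is then 53, 56 and 58% on 5, 6 and 7 df, and about 61% on 9 df. The comparison with 0.26 in Step 2 also precedes these reductions: in Scenario 1 the two-group figure would become 0.278/0.9 = 0.31.

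**Step 4: error rate if 1.96 is used in the analysis.** In a simulated single-time-point comparison of two of three groups, with twelve equal centres and the centre variance truncated at zero, type I error was roughly 6% at ICC 0.01, a little over 7% at 0.02 and about 8% at 0.05.

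**Step 5: the section 2.4 model.** A random centre intercept that is constant over time is the same at T0 and T2, so it cancels from the group*time contrast. Without a centre-by-time term the model carries no between-centre variance in change, and software may give that contrast child-level df. Asking for centre-based df without such a term would therefore not by itself solve the problem.

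**The case against.** The strongest objection is that the calculation is cruder than the analysis. It uses a cross-sectional SD and no baseline, whereas section 2.4 uses T0, T1 and T2 and baseline covariates. If baseline explained the same share r² of variance within and between centres, the noncentrality would be 2.80/√(1 − r²). On 9 df, power at the stated d would be about 74% at r = 0.3, 82% at 0.5 and 88% at 0.6; on 5, 6 and 7 df it would be about 80, 83 and 85% at r = 0.6. This stands as a limit on the point: a reader might infer that the planned mixed model has only 61 to 70% power, and the documents do not show that. Nor does the argument restore the stated figure, since no baseline–follow-up correlation is given and section 2.2 describes an unadjusted comparison.

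It is also fair that the plan's arithmetic is internally correct. The fault lies in the reference distribution, not in the sum.

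A reader might further infer that the feasibility argument collapses. It does not: before dropout and relative efficiency, only Scenario 1 on 5 df exceeds 0.26, and on 9 df all three scenarios stay below it. Nor do the documents plan an inflated type I error. They state no df method, so this is an omission.

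Finally, the scenarios are illustrative, all of the roughly 685 eligible children are invited, and the Summary lists BMI effects among the secondary objectives. That lowers the severity but does not justify the 80%.

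**Conclusion.** The point holds for the calculation in section 2.2. With the plan's ICC, SD, m and centres × m, power at the stated differences is about 61, 65 and 67% for the two-group contrast on 7, 8 and 9 centres. The figure of about 70% applies only if all twelve centres estimate the centre variance; it does not belong to the 7-to-9-centre contrast, and 9 df has not been shown to apply to the group*time contrast in section 2.4. If the listed dropout and relative efficiency still have to be taken off, power is about 53 to 58%, or 61% on 9 df. The result is conditional on centre-level df, which the documents neither specify nor exclude, and on an unadjusted two-year comparison. It should be fixed, but it does not call the study's main implementation objective into question.

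**What to change.** 1. **Section 2.2.** Recompute the three scenarios with t quantiles on centre-level df, and state which df are used. Use one consistent set of group sizes, and apply dropout and relative efficiency explicitly. Then restate either the power or the detectable differences, and revise the Scenario 1 feasibility sentence if the result requires it. The 0.28/0.24/0.22 and 0.25/0.22/0.21 above should not be inserted as they stand, because they omit both reductions. If credit is taken for baseline adjustment, state the assumed baseline–follow-up correlation and show a range.

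2. **Section 2.4.** State that the two-year group contrast is tested with centre-level denominator df. Add a centre-by-time random term, or specify an equivalent analysis of centre-level two-year change. Apply this to both the linear and the logistic models.

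The cost is wording and a short recalculation. No extra children or measurements are needed; the stated figures become less favourable.

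### The detectable effects in section 2.2 leave out the 10% dropout and 90% relative efficiency said to have been used, and do not rest on the listed arm sizes in Scenarios 1 and 3

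*Combined protocol and SAP*

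**What the plan says.** The calculation is in section 2.2, under Number of anticipated participants. It opens its list of inputs with "The following general assumptions were used for the sample size calculation". The list gives an independent-samples t-test, alpha 0.05, power 80%, an intraclass correlation of 0.01 and an SD of 0.60. It also includes "A dropout rate of 10" per cent and "Unequal cluster sizes with a relative efficiency of 90" per cent.

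Three scenarios follow. Scenario 1 has "three childcare centres, number of participants (N1)=120" for innovators/early adopters, "four childcare centres, number of participants (N3)=220" for laggards, and "Average size of each cluster (m): 50". Scenario 2 has four centres and 217 children in each group, with m = 55. Scenario 3 has four centres with 217 children against five centres with 303, again with m = 55.

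Each result is introduced by "With these assumptions we can demonstrate a" Cohen's d of a given size. Scenario 1 reports a Cohen's "d of 0.369, which means we can detect medium effect sizes on absolute BMI z-scores"; Scenarios 2 and 3 give 0.331 and 0.314. These are converted to differences of 0.22, 0.20 and 0.19 in absolute BMI z-score. Each difference is called feasible because a cited school-based study found 0.26.

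**The concern.** The text presents each d as the product of the full list of assumptions. A 10% dropout and a 90% relative efficiency would each raise the detectable d, so a reader takes the printed values as already discounted. If they are not, the plan overstates its power for the primary outcome, and a null result could be read as stronger evidence of no difference than it is.

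The listed sample sizes also do not agree with the number of centres times m. In Scenario 1, three centres at m = 50 make 150, not 120, and four make 200, not 220. In Scenario 3, five centres at m = 55 make 275, not 303. It is therefore unclear which sizes produced the results.

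**Working it through.** **Inputs** (all from section 2.2): alpha 0.05, power 80%, ICC 0.01, SD 0.60, dropout 10%, relative efficiency 90%, and N1, N3, m and the number of centres per scenario. Sidedness is not stated. I take alpha as two-sided, since the research questions in section 1.1 ask whether there is a difference.

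**Formulas**

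- SE(d) = sqrt{[1 + (m1 − 1) × 0.01]/N1 + [1 + (m3 − 1) × 0.01]/N3}
- detectable d = (1.960 + 0.842) × SE; difference in z = 0.60 × d
- power at a given d = Φ(d/SE − 1.960)

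**Step 1: reproduce the printed values.** Use centres × m as arm sizes and no allowance. The design effect is 1.49 for m = 50 and 1.54 for m = 55.

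- Scenario 1: sqrt[1.49 × (1/150 + 1/200)] = 0.1319; d = 0.3694
- Scenario 2: sqrt[1.54 × (1/220 + 1/220)] = 0.1183; d = 0.3315
- Scenario 3: sqrt[1.54 × (1/220 + 1/275)] = 0.1122; d = 0.3145

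With the rounded multiplier 1.96 + 0.84 = 2.80 these become 0.3692, 0.3313 and 0.3143, which round to the printed 0.369, 0.331 and 0.314. Adding both allowances to the same arm sizes (m unchanged) gives 0.410, 0.368 and 0.349. Adding a single factor of 0.9 gives 0.389, 0.349 and 0.331. Neither set matches.

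**Step 2: listed Ns, still without allowances.** The ranges take m either as printed or as the listed average per arm (40 and 55; 54.25; 54.25 and 60.6).

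| Scenario | Arms in the printed result | Arms listed | d from listed Ns | Power at printed d |
|---|---|---|---|---|
| 1 | 150/200 | 120/220 | 0.382-0.388 | 76-77% |
| 2 | 220/220 | 217/217 | 0.333-0.334 | 79-80% |
| 3 | 220/275 | 217/303 | 0.309-0.311 | 81% |

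The mismatch flatters Scenario 1, is trivial in Scenario 2, and is slightly conservative in Scenario 3.

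**Step 3: listed Ns with both allowances.** Each N is multiplied by 0.9 × 0.9 = 0.81, treating relative efficiency as a reduction in effective sample size. Dropout also shrinks clusters, so m becomes 45 or 49.5 and the design effect 1.44 or 1.485.

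- Scenario 1: sqrt[1.44 × (1/97.2 + 1/178.2)] = 0.1513; d = 0.424; difference 0.254; power at 0.369 = Φ(0.369/0.1513 − 1.960) = 68%
- Scenario 2: sqrt[1.485 × (2/175.77)] = 0.1300; d = 0.364; difference 0.219; power at 0.331 = 72%
- Scenario 3: sqrt[1.485 × (1/175.77 + 1/245.43)] = 0.1204; d = 0.337; difference 0.202; power at 0.314 = 74%

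Varying m (printed or arm average, held fixed or cut by 10%) gives these ranges:

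| Scenario | Printed difference | Detectable difference | Power at printed d | Power at 0.26 z |
|---|---|---|---|---|
| 1 | 0.22 | 0.251-0.259 | 67-70% | 80-83% |
| 2 | 0.20 | 0.218-0.223 | 71-72% | 91-92% |
| 3 | 0.19 | 0.202-0.207 | 72-74% | 94-95% |

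Using centres × m with both allowances instead gives 0.242-0.246, 0.217-0.221 and 0.206-0.210 z, with 71-73% power at the printed d.

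**The case against.** **The Ns may already be net of losses.** The text does not say whether they count enrolled or analysed children.

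- *Net of dropout only.* Scenario 3 would need 520/0.9 = 578 of the roughly 685 eligible children in nine centres, leaving 107 for the other three (36 each). This is possible. The 90% efficiency would still be missing: on the listed Ns with efficiency alone, the differences are 0.242-0.246, 0.211 and 0.196-0.197 z, with 71-77% power at the printed d.
- *Net of both.* Nothing would then be omitted, and only the arm-size mismatch of Step 2 would remain. But a count labelled as participants would have to be an effective sample size. Scenario 3 would also need 520/0.81 = 642 children in nine centres, leaving 43 for the other three (14 each). Scenario 1 alone would not rule this reading out. Taken as gross, Scenario 3 leaves (685 − 520)/3 = 55 per remaining centre, which matches m.

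**Alpha may be one-sided.** With both allowances on centres × m, one-sided alpha gives 0.364, 0.327 and 0.310. These are near the printed values but miss all three, whereas the two-sided calculation without allowances matches all three. The arm-size mismatch would remain.

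**The practical effect is limited.** This stands. The scenarios are illustrations, since centres are categorised only after data collection. All eligible children are invited, so no recruitment number depends on the result. The mixed model in section 2.4 may gain precision from baseline variables, which this calculation does not address.

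**Conclusion.** The concern holds. The printed d values are those of a calculation with neither dropout nor relative efficiency, on arm sizes that are not the listed ones in Scenarios 1 and 3. Under the plan's own assumptions and listed Ns, detectable differences are about 0.25-0.26, 0.22 and 0.20-0.21 z, and power at the printed d is 67-74%, against the stated 80%.

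This assumes two-sided alpha, Ns that count enrolled children, and relative efficiency acting as a factor on effective sample size. If the Ns are net of dropout, power is 71-77%. The reading under which no allowance is missing is unlikely and unsupported by the text.

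The feasibility statement is not overturned: power at 0.26 z is at least 80% in every scenario. In Scenario 1, however, the margin below 0.26 shrinks from 0.04 to between 0.001 and 0.009. This should be fixed as an error in the stated calculation; it is not a flaw in the design.

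**What to change.** In section 2.2:

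1. Reconcile N1, N3 and m in each scenario, and state whether they count enrolled or analysed children.
2. State that alpha is two-sided, if that is intended.
3. Apply the 10% dropout (to m as well as N) and the 90% relative efficiency. Restate the detectable differences, about 0.25-0.26, 0.22 and 0.20-0.21 z on the listed Ns taken as enrolled, or give the power at the printed d.
4. If the Ns are already net of dropout, say so, correct them where they disagree with centres × m, and still apply the 90% efficiency. If they are claimed to be net of both, show the gross numbers they came from.
5. Keep the feasibility sentence, but add for Scenario 1 that the margin against 0.26 is small.

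A sensitivity line for the small number of centres compared (seven to nine) would be useful but is optional.

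The cost is a recalculation and some rewording, with less favourable stated figures. It needs no extra children and no design change.
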